2.2 Other criteria

None.

[figure not shown]
2.3 Analysis sets

ENROLLED PATIENTS: All patients entered in eCRF.

ELIGIBLE PATIENTS (UNCOMMON MUTATION COHORT): All enrolled patients meeting all the criteria described in section 2.1 (considering the UNCOMMON MUTATION COHORT version of criteria, where applicable) and in section 2.2.

ELIGIBLE PATIENTS (SEQUENCING COHORT): All enrolled patients meeting all the criteria described in section 2.1 (considering the SEQUENCING COHORT version of criteria, where applicable) and in section 2.2.

The analyses will be done on patients who respond to inclusion/exclusion criteria and are evaluable for primary analysis (i.e. patients without available data for the primary analysis will NOT be classified as "ELIGIBLE"), unless differently specified (see Chapter 4).

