9.7 DATA ANALYSIS

The two cohorts will be analysed separately

- Uncommon mutations
- Sequencing of osimertinib after afatinib

The primary endpoint for both cohorts is time on treatment. Kaplan-Meier estimates will be calculated. In addition, the median will be tabulated along with the two-sided 95% confidence interval, using Greenwood's variance estimate.

The following additional endpoints will be analyzed similarly to the primary endpoint.

- overall survival
- time on treatment until failure of second-line (uncommon cohort only)

Patients who were not known to have discontinued treatment will be censored on the date they were last verified to have been on treatment.

A second round of data collection for additional follow-up may be performed in case a substantial proportion of patients had not discontinued treatment before the estimated median time on treatment at the time of the primary data collection.

Best overall response will be tabulated, as will the following:

- demographics
- disease characteristics
- methodology and material used for mutation classification
- anti-cancer drugs used prior to, or after EGFR-TKI (uncommon cohort only).

These endpoints will be analyzed descriptively.

Within the sequencing cohort, the proportion of patients with different types of resistance mutations observed at the time of discontinuation of osimertinib will be categorized and tabulated.

In this study, data will be gathered retrospectively from patients treated within the conditions of the approved marketing authorization of afatinib. Drug exposure during pregnancy, ADRs with causality to Gilotrif (serious or non-serious) and all fatal AEs will be reported to PV on the NIS AE form - excluding deaths to PD of the underlying malignancy. Safety data will be reviewed and analysed as part routine global pharmacovigilance procedures. All adverse events/reactions collected for the study per protocol will be summarised in the final study report.

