3 COMPUTED VARIABLES

The following variables will be computed as described below.

In this section, the eCRF fields are indicated as: "label of the field" [*name of the time point / name of the form. name of the eCRF variable*].

In case of partial dates (i.e. day and/or month not known), the Biostatistician will estimate incomplete dates to be used in the statistical analysis as follows: if year is not unknown, missing days will be inputed as the first day of the month (01) and month will be inputed as "July" (07).

Moreover, if a patient is deceased and in the eCRF it is not reported that the patient stopped a specific treatment (ie. the treatment stop date is not provided), then the treatment stop date will be imputed with the date of death.

Number of NSCLC treatment lines and type of lines

For each patient, the total number of NSCLC treatment lines will be calculated as follows:

- If "Number of treatment lines for advanced EGFR-mutated NSCLC within date of data collection" [*PI. PI_num_lines*] = "1", this will correspond also to the total number of lines (this options is applicable only for UNCOMMON MUTATION COHORT). By definition, the line shall be an EGFR-TKI, and the type of treatment will be retrieved in field "Type of EGFR-TKI" [*EAD. EAD_EGFR*].
- If "Number of treatment lines for advanced EGFR-mutated NSCLC within date of data collection" [*PI. PI_num_lines*] = "2", depending on the type of cohort
 - *Uncommon mutation cohort*:
 1. the first-line treatment will be retrieved from the field [*First-line treatment period / TREAT. TREAT_ty*], and in case it is an "EGFR-TKI" the exact therapy will be retrieved from the field "Type of EGFR-TKI" [*EAD. EAD_EGFR*] of the record of the EGFR-TKI ADMINISTRATION DETAILS form having "Start date with this dose (dd/mmm/yyyy)" [*EAD. EAD_start_date*] equal to "Start date of this line (dd/mmm/yyyy)" [*First-line treatment period / TREAT. TREAT_start_date*];
 2. the second-line treatment will be retrieved from the field [*Second-line treatment period / TREAT. TREAT_ty*], and in case it is an "EGFR-TKI" the exact therapy will be retrieved from the field "Type of EGFR-TKI" [*EAD. EAD_EGFR*] of the record of the EGFR-TKI ADMINISTRATION DETAILS form having "Start date with this dose (dd/mmm/yyyy)" [*EAD. EAD_start_date*] equal to "Start date of this line (dd/mmm/yyyy)" [*Second-line treatment period / TREAT. TREAT_start_date*].

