- patients' distribution (absolute and relative frequency) by number of NSCLC lines prior to the index EGFR-TKI therapy (that will be obtained considering the ordinal number of the index EGFR-TKI therapy, as defined in the "Computed variables" chapter);
- patients' distribution (absolute and relative frequency) by pattern of NSCLC treatment prior to the index EGFR-TKI therapy (see "Computed variables" chapter) considering only the sequence of NSCLC treatments until the index EGFR-TKI therapy (excluded).

Descriptives and percentages will be calculated over the number of ELIGIBLE PATIENTS in the cohort.

Table 34-UNC. Index EGFR-TKI therapy patterns (ELIGIBLE PATIENTS of the Uncommon Mutation Cohort)

The table will provide:

- patients' distribution (absolute and relative frequency) by ordinal number of line of the index EGFR-TKI therapy (see "Computed variables" chapter);
- patients' distribution (absolute and relative frequency) by type of NSCLC treatment patterns (see "Computed variables" chapter) considering only the sequence of NSCLC treatments from the index EGFR-TKI therapy thereafter.

Descriptives and percentages will be calculated over the number of ELIGIBLE PATIENTS in the cohort.

Table 35-UNC. Response to index EGFR-TKI treatment (ELIGIBLE PATIENTS of the Uncommon Mutation Cohort) – Secondary objective #1

The table will provide:

- absolute and relative frequency of "Best response achieved" [**First-line treatment period or Second-line treatment period / RESP. RESP_best**, depending on which is the index-line];
- absolute and relative frequency of patients achieving Overall Response (ORR), ie. those with [**First-line treatment period or Second-line treatment period / RESP. RESP_best**] = "Complete response (CR)" or "Partial Response (PR)";
- descriptive statistics (mean, standard deviation, quartiles, min, max) of Duration of response (in months) [**First-line treatment period or Second-line treatment period / RESP. RESP_dur_num, RESP_dur_unit**] for patients achieving Overall Response (ORR) (as defined before); all units will be reported to months.

Descriptives and percentages will be calculated over the number of ELIGIBLE PATIENTS in the cohort, unless differently specified.

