4.1.6 Overall Survival – Secondary objective #2

Table 38-UNC. Overall Survival with index therapy EGFR-TKI (ELIGIBLE PATIENTS of the Uncommon Mutation Cohort)

The table will provide the Kaplan-Meier estimates of quartiles of time to death (with their 95% Confidence Intervals, using Greenwood's variance estimate) (see algorithm for Overall Survival in the "Computed variables" chapter).

Moreover, a Kaplan-Meier survival curve will be provided. The analysis will be represented on a plot having the time to event on the horizontal axis and the percentage of event-free patients on the vertical axis.

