4.2.4 NSCLC treatments

Table 15-SEQ. NSCLC treatment patterns (ELIGIBLE PATIENTS of the Sequencing Cohort)

See corresponding table for the UNCOMMON MUTATION COHORT. However, the results will be focused on the 3rd or subsequent lines (if any), since the whole cohort will have in common the initial pattern “afatinib→osimertinib” by definition.

Table 16-SEQ. Details of first-line EGFR-TKI treatment (afatinib) (ELIGIBLE PATIENTS of the Sequencing Cohort)

The table will provide:

- absolute and relative frequency of afatinib starting daily dose (mg) (see “Computed variables” chapter).
- descriptive statistics (mean, standard deviation, quartiles, min, max) of Duration of afatinib treatment (see “Computed variables” chapter).

Descriptives and percentages will be calculated over the number of ELIGIBLE PATIENTS in the cohort.

Table 17-SEQ. Response to first-line treatment (afatinib) (ELIGIBLE PATIENTS of the Sequencing Cohort) – Secondary objective #1

See corresponding table for the UNCOMMON MUTATION COHORT.

Table 18-SEQ. Details of second-line EGFR-TKI treatment (osimertinib) (ELIGIBLE PATIENTS of the Sequencing Cohort)

The table will provide:

- absolute and relative frequency of osimertinib starting daily dose (mg) (see “Computed variables” chapter)
- patients’ distribution (absolute and relative frequency) by “Which programme was used for patient treatment with osimertinib?” [[Second-line treatment period / TREAT.TREAT_osim_progr](#)]
- descriptive statistics (mean, standard deviation, quartiles, min, max) of Duration of osimertinib treatment (see “Computed variables” chapter)

Descriptives and percentages will be calculated over the number of ELIGIBLE PATIENTS in the cohort.

Table 19-SEQ. Response to second-line treatment (osimertinib) (ELIGIBLE PATIENTS of the Sequencing Cohort) – Secondary objective #1

See corresponding table for the UNCOMMON MUTATION COHORT.

Moreover, the table will provide patients’ distribution (absolute and relative frequency) by “Presence of brain metastases at the end of osimertinib treatment line?” [[Second-line treatment period / RESP.RESP_brain_met](#)].

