4.2.6 Overall Survival

Table 21-SEQ. Overall Survival from afatinib start (ELIGIBLE PATIENTS of the Sequencing Cohort) - Secondary objective #2

The table will provide the Kaplan-Meier estimates of quartiles of time to death from afatinib start (with their 95% Confidence Intervals, using Greenwood's variance estimate) (see algorithm for Overall Survival in the "Computed variables" chapter).

Moreover, a Kaplan-Meier survival curve will be provided. The analysis will be represented on a plot having the time to event on the horizontal axis and the percentage of event-free patients on the vertical axis.

Table 22-SEQ. Overall Survival from osimertinib discontinuation (ELIGIBLE PATIENTS of the Sequencing Cohort)

[figure not shown]
The table will provide the Kaplan-Meier estimates of quartiles of time to death from osimertinib discontinuation (with their 95% Confidence Intervals, using Greenwood's variance estimate) (see algorithm for Overall Survival in the "Computed variables" chapter).

Moreover, a Kaplan-Meier survival curve will be provided. The analysis will be represented on a plot having the time to event on the horizontal axis and the percentage of event-free patients on the vertical axis.

In this analysis, only patients who discontinued osimertinib (see "Computed variables" chapter) will be considered.

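### Evaluability for time on treatment is built into ELIGIBLE, so a living patient with an undatable discontinuation also leaves the OS, response and mutation-testing tables, while a deceased one stays

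*SAP*

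**What the plan says.** SAP 2.3 first defines ELIGIBLE for each cohort as meeting the criteria in 2.1 and 2.2; section 2.2 lists none. Its closing paragraph then adds that "patients without available data for the primary analysis will NOT be classified as" ELIGIBLE, with the proviso "unless differently specified (see Chapter 4"). The note under Table 1-UNC in SAP 5.1.1 describes eligible patients by inclusion and exclusion criteria alone.

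The secondary tables are built on that set:
- OS: "Table 38-UNC. Overall Survival with index therapy EGFR-TKI (ELIGIBLE PATIENTS of the Uncommon Mutation Cohort") and "Table 21-SEQ. Overall Survival from afatinib start (ELIGIBLE PATIENTS of the Sequencing Cohort").
- Response: "Table 35-UNC. Response to index EGFR-TKI treatment (ELIGIBLE PATIENTS of the Uncommon Mutation Cohort") and "Table 19-SEQ. Response to second-line treatment (osimertinib) (ELIGIBLE PATIENTS of the Sequencing Cohort").
- Mutation testing: Tables 10-, 13- and 16-UNC, and 10- and 12-SEQ.

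No visible text in Chapter 4 restores the removed patients for any of these.

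On missing stop dates, SAP Chapter 3 says that for a deceased patient with none recorded, "then the treatment stop date will be imputed with the date of death". Partial dates are completed for everyone, provided that the year is known. Chapter 4, by contrast, opens with a variable-by-variable rule: no imputation, and a patient with a missing value is left out only of analyses of that variable.

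**The concern.** OS and response do not depend on when the index drug was stopped. OS needs a treatment start date and a date of death, data collection or last known alive. Response needs the recorded best response. Making evaluability for the primary endpoint part of the set definition therefore discards usable secondary data because a different variable is missing.

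If the removed patients are all alive or untraceable, the removal also selects on the outcome that OS measures. The death share in the remaining set rises and OS reads too low. SAP Chapter 1 allows deceased and untraceable patients to be enrolled specifically to avoid selection bias, so a rule that reintroduces selection by vital status works against the plan's own intention.

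**Working it through.** **Step 1: trace each class of patient.** The rules are the partial-date and death-date rules and the two time-on-treatment definitions in SAP Chapter 3. The start date is taken as known.

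| Vital status | Treatment discontinued? | Stop date | Result |
|---|---|---|---|
| Deceased | any | known or missing | kept: death is an event, and a missing stop date becomes the date of death |
| Living or untraceable | No | not needed | kept: censored at end of observation |
| Living or untraceable | UNK | not needed | kept: censored at the latest dose-record start date |
| Living or untraceable | Yes | at least the year | kept: event, partial date completed |
| Living or untraceable | Yes | no year | no rule |
| Living or untraceable | blank | none | no rule |

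Only the last two rows lack primary-analysis data. Under SAP 2.3 these patients are not ELIGIBLE, so they leave the OS, response and mutation-testing tables.

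**Step 2: size the class.** The plan gives no figure to reproduce. The only maturity figures are those of the earlier real-world sequencing study in Protocol 7.2: 52% for time to treatment failure and 31% for OS. Assume that they carry over and that every death is also a treatment-failure event:

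living and off treatment = 52% − 31% = 21% of the cohort.

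Let q be the share of these with no stop year (assumed).

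| q | Share of cohort lost, 0.21 × q | Lost of 200 | Death share, 0.31 / (1 − 0.21 × q) |
|---|---|---|---|
| 5% | 1.05% | 2.1 | 31.3% |
| 10% | 2.1% | 4.2 | 31.7% |
| 20% | 4.2% | 8.4 | 32.4% |
| 50% | 10.5% | 21.0 | 34.6% |

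**Step 3: effect on OS.** This is a Kaplan-Meier simulation of 400,000 patients. Inputs from the Protocol are 2-year survival of 79% in the earlier study (7.2) and a projected 30-month median time on treatment (9.5). Assumptions are exponential times, death independent of discontinuation, and follow-up uniform over 20 to 60 months. The monthly death hazard is −ln(0.79)/24. The hazard of stopping or dying is ln(2)/30, and the hazard of stopping while alive is the difference.

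| q | 24-month OS | 36-month OS |
|---|---|---|
| 0 | 79.0% | 70.2% |
| 5% | 78.7% | 69.8% |
| 10% | 78.4% | 69.3% |
| 20% | 77.8% | 68.4% |
| 50% | 75.7% | 65.4% |

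In the simulation 26.7% of patients are alive and off treatment, against 21% in Step 2. It therefore loses 1.34% of the cohort at q = 5% and 5.34% at q = 20%, and slightly overstates the shift that goes with the Step 2 counts.

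**Step 4: compare with precision.** For 200 patients and 24-month OS of 79%, ignoring censoring, the 95% half-width is 1.96 × √(0.79 × 0.21 / 200) = 5.6 percentage points. The shift at q = 5% to 20% is 79.0 − 78.7 = 0.3 to 79.0 − 77.8 = 1.2 points.

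**Step 5: response.** A removed patient leaves both numerator and denominator. Nothing in the documents says whether such patients responded more or less often than the rest, so no direction follows.

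**The case against.** The strongest reply is that the class is very small. Line start and stop dates are core data items (Protocol 9.3). The eCRF has automated completeness checks, and about 30% of patients undergo source verification (Protocol 9.8). Database lock needs the biostatistician and the sponsor to accept data quality in light of the primary and secondary objectives (SAP 6). A living patient known to have stopped, with not even a year recorded, should be rare. The study is descriptive, and one common denominator is a defensible preference. This stands as far as size goes. It does not explain why OS should depend on a variable that it does not use, or how the rule fits the variable-by-variable exclusion in Chapter 4.

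Three stronger readings are tempting, and the documents do not support them.
- A reader might infer that living patients in general are lost and deceased ones kept. The No and UNK rules and the completion of partial dates keep most living patients.
- A reader might infer that the death-date rule causes the loss. It removes nobody. Death by any cause is already an event, so a deceased patient has primary data without it.
- A reader might infer that these exclusions have no place in the reporting. SAP 4.1.1 says that Table 2 covers reasons for non-evaluability, and its layout is left open. The gap is in the 2.5 hierarchy, which covers only criteria 1 to 10 and drives Figure 1. Table 2 also refers to criteria in 2.3, whereas the numbered list is in 2.1.

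**Conclusion.** The point holds for a narrow class. SAP 2.3 makes primary evaluability a condition of ELIGIBLE, and that condition reaches secondary tables that do not need it, Table 22-SEQ excepted. For living or untraceable patients recorded as discontinued with no stop year, or with the field blank, membership depends on vital status. Their loss is inferred from 2.3 together with the absence of any rule for them; the SAP does not state it outright.

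The OS bias is downward and probably small: 0.3 to 1.2 percentage points at 24 months for q = 5% to 20%, well inside the sampling error at 200 patients. This rests on an assumed q, on maturity carried over from the earlier study, and on exponential times. That study followed the afatinib-osimertinib sequence, so the figures transfer less securely to the uncommon mutation cohort. A material bias would need missing stop years to be common, and no document suggests that.

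**What to change.** In SAP 2.3:
- Define ELIGIBLE by criteria 1 to 10 only (criterion 10 applies to the uncommon mutation cohort alone).
- Define a subset evaluable for time on treatment, and use it only for Tables 36-UNC and 20-SEQ.
- Run the OS, response and mutation-testing tables on all ELIGIBLE patients, in line with the Chapter 4 missing-data rule. Table 22-SEQ keeps its own restriction to patients with an osimertinib stop date.
- Add a line for patients not evaluable for time on treatment to Figure 1 and Table 2 in each cohort, and correct the Table 2 cross-reference.

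Do not bring the undatable stops back into the primary tables by censoring them. Protocol 9.7 says "Patients who were not known to have discontinued treatment will be censored on the date they were last verified to have been on treatment", which covers patients whose discontinuation is not known. A patient recorded as discontinued has had the event; treating it as censored would push the time-on-treatment estimate upward.

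The cost is SAP wording and two extra reporting lines, with no new data. Denominators will differ by a few patients between the primary and secondary tables, which a footnote can explain.

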2.5 Hierarchy of violated criteria

The purpose of this algorithm is to assign an unique, major criteria violation to each enrolled patients, even in case a patient has more than one reason (ie. more than one criterion) for being excluded from the analysis.

2.5.1 UNCOMMON MUTATION COHORT

- 1) Violation of **criterion 4** (as defined in Section 2.1) **for any reasons**: if informed consent/privacy consent was not provided where applicable by local regulations, patients' data cannot be used
- 2) Violation of **criterion 1** (as defined in Section 2.1) **for any reasons**: non-adult patients cannot be enrolled
- 3) Violation of **criterion 2** (as defined in Section 2.1) **where the violation is documented by the Investigator** (in the ELIGIBILITY CRITERIA form) **or in the PROTOCOL DEVIATION FORM**
- 4) Violation of **criterion 2** (as defined in Section 2.1) **for any other reason**
- 5) Violation of **criterion 3** (as defined in Section 2.1) **where the violation is documented by the Investigator** (in the ELIGIBILITY CRITERIA form) **or in the PROTOCOL DEVIATION FORM**
- 6) Violation of **criterion 3** (as defined in Section 2.1) **for any other reason**
- 7) Violation of **criterion 5** (as defined in Section 2.1) **where the violation is documented by the Investigator** (in the ELIGIBILITY CRITERIA form) **or in the PROTOCOL DEVIATION FORM**
- 8) Violation of **criterion 5** (as defined in Section 2.1) **for any other reason**
- 9) Violation of **criterion 6** (as defined in Section 2.1) **where the violation is documented by the Investigator** (in the ELIGIBILITY CRITERIA form) **or in the PROTOCOL DEVIATION FORM**
- 10) Violation of **criterion 6** (as defined in Section 2.1) **for any other reason**
- 11) Violation of **criterion 7** (as defined in Section 2.1) **where the violation is documented by the Investigator** (in the ELIGIBILITY CRITERIA form) **or in the PROTOCOL DEVIATION FORM**
- 12) Violation of **criterion 7** (as defined in Section 2.1) **for any other reason**
- 13) Violation of **criterion 8** (as defined in Section 2.1) **where the violation is documented by the Investigator** (in the ELIGIBILITY CRITERIA form) **or in the PROTOCOL DEVIATION FORM**
- 14) Violation of **criterion 8** (as defined in Section 2.1) **for any other reason**
- 15) Violation of **criterion 9** (as defined in Section 2.1) **where the violation is documented by the Investigator** (in the ELIGIBILITY CRITERIA form) **or in the PROTOCOL DEVIATION FORM**
- 16) Violation of **criterion 9** (as defined in Section 2.1) **for any other reason**
- 17) Violation of **criterion 10** (as defined in Section 2.1) **where the violation is documented by the Investigator** (in the ELIGIBILITY CRITERIA form) **or in the PROTOCOL DEVIATION FORM**
- 18) Violation of **criterion 10** (as defined in Section 2.1) **for any other reason**

2.5.2 SEQUENCING COHORT

The same algorithm will be used also for SEQUENCING COHORT, but criterion 10 will not be applicable.

3 COMPUTED VARIABLES

The following variables will be computed as described below.

In this section, the eCRF fields are indicated as: "label of the field" [*name of the time point / name of the form. name of the eCRF variable*].

In case of partial dates (i.e. day and/or month not known), the Biostatistician will estimate incomplete dates to be used in the statistical analysis as follows: if year is not unknown, missing days will be inputed as the first day of the month (01) and month will be inputed as "July" (07).

Moreover, if a patient is deceased and in the eCRF it is not reported that the patient stopped a specific treatment (ie. the treatment stop date is not provided), then the treatment stop date will be imputed with the date of death.

Number of NSCLC treatment lines and type of lines

For each patient, the total number of NSCLC treatment lines will be calculated as follows:

- If "Number of treatment lines for advanced EGFR-mutated NSCLC within date of data collection" [*PI. PI_num_lines*] = "1", this will correspond also to the total number of lines (this options is applicable only for UNCOMMON MUTATION COHORT). By definition, the line shall be an EGFR-TKI, and the type of treatment will be retrieved in field "Type of EGFR-TKI" [*EAD. EAD_EGFR*].
- If "Number of treatment lines for advanced EGFR-mutated NSCLC within date of data collection" [*PI. PI_num_lines*] = "2", depending on the type of cohort
 - *Uncommon mutation cohort*:
 1. the first-line treatment will be retrieved from the field [*First-line treatment period / TREAT. TREAT_ty*], and in case it is an "EGFR-TKI" the exact therapy will be retrieved from the field "Type of EGFR-TKI" [*EAD. EAD_EGFR*] of the record of the EGFR-TKI ADMINISTRATION DETAILS form having "Start date with this dose (dd/mmm/yyyy)" [*EAD. EAD_start_date*] equal to "Start date of this line (dd/mmm/yyyy)" [*First-line treatment period / TREAT. TREAT_start_date*];
 2. the second-line treatment will be retrieved from the field [*Second-line treatment period / TREAT. TREAT_ty*], and in case it is an "EGFR-TKI" the exact therapy will be retrieved from the field "Type of EGFR-TKI" [*EAD. EAD_EGFR*] of the record of the EGFR-TKI ADMINISTRATION DETAILS form having "Start date with this dose (dd/mmm/yyyy)" [*EAD. EAD_start_date*] equal to "Start date of this line (dd/mmm/yyyy)" [*Second-line treatment period / TREAT. TREAT_start_date*].
 - *Sequencing cohort*: by definition, "Afatinib" will be the first-line treatment, and "Osimertinib" will be the second-line treatment.
- If "Number of treatment lines for advanced EGFR-mutated NSCLC within date of data collection" [*PI. PI_num_lines*] = ">2", the first-line and second-line definition will correspond to those defined for patients with 2 lines only, while the subsequent lines will be retrieved from the records of the SUBSEQUENT LINES DETAILS form [*name of the form: SLD*]. In particular, each record will correspond to a single NSCLC therapy line, which will be identified on the basis of the field "Type of treatment" [*SLD. SLD_treat, SLD_EGFR*] after having ordered by "Start date of this line (dd/mmm/yyyy)" [*SLD. SLD_start_date*] (ascending order).

Start date of first-line therapy

- *Uncommon mutation cohort*: it will correspond to the therapy recorded in the NSCLC TREATMENT form at [*First-line treatment period*] according to the field: "Start date of this line (dd/mmm/yyyy)" [*First-line treatment period / TREAT. TREAT_start_date*]
- *Sequencing cohort*: it will correspond to the therapy recorded in the AFATINIB ADMINISTRATION DETAILS form, having the earliest non-missing date recorded in field "Start date with this dose (dd/mmm/yyyy)" [*AAD. AAD_start_date*].

Type of NSCLC treatment patterns for UNCOMMON MUTATION COHORT

Patient's treatment patterns will be defined according to the data recorded in the following forms:

- NSCLC TREATMENT at [*First-line treatment period*], considering the concatenation of fields [**TREAT**.
TREAT_ty (*), **TREAT_ty_sp**, **TREAT_radio_YN**]. The start date of this line will correspond to the field [*First-line treatment period / TREAT. TREAT_start_date*], while the stop date of this line (if any) will correspond to the field [*First-line treatment period / TREAT. TREAT_stop_date*];
- NSCLC TREATMENT at [*Second-line treatment period*] (if applicable, for patients with Number of NSCLC treatment lines (as defined before) >1), considering the concatenation of fields [**TREAT**.
TREAT_ty (**), **TREAT_ty_sp**, **TREAT_radio_YN**]. The start date of this line will correspond to the field [*Second-line treatment period / TREAT. TREAT_start_date*], while the stop date of this line (if any) will correspond to the field [*Second-line treatment period / TREAT. TREAT_stop_date*].
- SUBSEQUENT LINES DETAILS (if applicable, for patients with Number of NSCLC treatment lines (as defined before) >2), considering the concatenation of fields [**SLD**.
SLD_treat (***) , **SLD_treat_sp**, **SLD_radio_YN**]. The start date of this line will correspond to the field [**SLD**.
SLD_start_date], while the stop date of this line (if any) will correspond to the field [**SLD**.
SLD_stop_date]. *The same patient could have more than one record: each record corresponds to a distinct line, which shall be ordered by start date.*

(*) in case it is an "EGFR-TKI", the exact therapy will be retrieved from the field "Type of EGFR-TKI" [**EAD**.
EAD_EGFR] of the record of the EGFR-TKI ADMINISTRATION DETAILS form having "Start date with this dose (dd/mmm/yyyy)" [**EAD**.
EAD_start_date] equal to "Start date of this line (dd/mmm/yyyy)" [*First-line treatment period / TREAT. TREAT_start_date*].

(**) in case it is an "EGFR-TKI" the exact therapy will be retrieved from the field "Type of EGFR-TKI" [**EAD**.
EAD_EGFR] of the record of the EGFR-TKI ADMINISTRATION DETAILS form having "Start date with this dose (dd/mmm/yyyy)" [**EAD**.
EAD_start_date] equal to "Start date of this line (dd/mmm/yyyy)" [*Second-line treatment period / TREAT. TREAT_start_date*].

(***) in case it is an "EGFR-TKI", the exact therapy will be retrieved from the field "Type of EGFR-TKI" [**SLD**.
SLD_EGFR] of the same record.

Having defined the start and end dates of each line, the **Duration of treatment lines** will be calculated as the difference between the stop date of the line (^) and the start date of the line + 1 day.

(^) or the end of observation date (as defined later), in case the therapy line was not discontinued at the end of observation.

*In particular, for each patient, the sequences of treatments will be defined taking into consideration the start dates of each line (as defined before). This way, it will be possible to calculate also the **ordinal number** of each line.* Here below are provided some examples of the treatment line sequence that might be observed:

- EGFR-TKI (afatinib)
- Chemotherapy+Radiotherapy → EGFR-TKI (erlotinib)
- Chemotherapy+Targeted therapy → EGFR-TKI (gefitinib) → Chemotherapy+Immunotherapy
- etc.

Type of NSCLC treatment patterns for SEQUENCING COHORT

Patient's treatment patterns will be defined as follows:

- by definition, "Afatinib" will be the first-line treatment; the start date of the line will be the earliest start date of the field [AAD. AAD_start_date], while the stop date of the line will be the greatest stop date of the field [AAD. AAD_stop_date];
- by definition, "Osimertinib" will be the second-line treatment; the start date of the line will be the earliest start date of the field [OAD. OAD_start_date], while the stop date of the line will be the greatest stop date of the field [OAD. OAD_stop_date];
- subsequent lines will be defined according to the data recorded in the following forms SUBSEQUENT LINES DETAILS (if applicable, for patients with Number of NSCLC treatment lines (as defined before) >2), considering the concatenation of fields [SLD. SLD_treat (**), SLD_treat_sp, SLD_radio_YN]. The start date of this line will correspond to the field [SLD. SLD_start_date]. *The same patient could have more than one record: each record corresponds to a distinct line, which shall be ordered by start date.*

(***) in case it is an "EGFR-TKI", the exact therapy will be retrieved from the field "Type of EGFR-TKI" [SLD. SLD_EGFR] of the same record.

Having defined the start and end dates of each line, the **Duration of treatment lines** will be calculated as the difference between the stop date of the line (^) and the start date of the line + 1 day.

(^) or the end of observation date (as defined later), in case the therapy line was not discontinued at the end of observation.

*In particular, for each patient, the sequences of treatments will be defined taking into consideration the start dates of each line (as defined before). This way, it will be possible to calculate also the **ordinal number** of each line.*

EGFR-TKI generation

- "Erlotinib" and "Gefitinib" will be classified as "1st generation EGFR-TKI";
- "Afatinib" will be classified as "2nd generation EGFR-TKI";
- "Osimertinib" will be classified as "3rd generation EGFR-TKI".

EGFR-TKI starting daily dose (mg) (first- and second-line treatment only)

The starting dose will be retrieved from the following fields of the following forms:

- from the AFATINIB ADMINISTRATION DETAILS form (only for the SEQUENCING COHORT), from the field [AAD. AAD_dose] of the record with earliest non-missing start date (recorded in field [AAD. AAD_start_date]);
- from the OSIMERTINIB ADMINISTRATION DETAILS form (only for the SEQUENCING COHORT), from the field [OAD. OAD_dose] of the record with earliest non-missing start date (recorded in field [OAD. OAD_start_date]);
- from the EGFR-TKI ADMINISTRATION DETAILS form (only for the UNCOMMON MUTATION COHORT), from the field [EAD. EAD_dose] of the record with earliest non-missing start date (recorded field [EAD. EAD_start_date]). The same patient could have one or two lines of EGFR-TKI recorded in this form, and each line is identified by the field "Type of EGFR-TKI" [EAD. EAD_EGFR]: therefore, for each line recorded in this form, it will be possible to identify the starting dose with the rule defined above.

Index EGFR-TKI therapy

- *Uncommon mutation cohort*: it will correspond to the therapy recorded in the NSCLC TREATMENT form, either at [First-line treatment period] or [Second-line treatment period] depending on the following conditions:
 - [First-line treatment period] is the time point to consider if:
 - “Type of treatment” [First-line treatment period / TREAT. TREAT_ty] = “EGFR-TKI” AND
 - “Start date of this line (dd/mmm/yyyy)” [First-line treatment period / TREAT. TREAT_start_date] is lower than or equal to (“Date of data collection (dd/mmm/yyyy)” [PI. PI_date_coll] – 11.50 months) AND
 - “EGFR mutations at start of first-line treatment” [First-line treatment period / MUT1. MUT1_unc] has at least one of the options selected (excluding “Del19” and “L858R”) (*)
 - Otherwise, if the above-specified condition is not met, then the [Second-line treatment period] is the time point to consider if:
 - “Type of treatment” [Second-line treatment period / TREAT. TREAT_ty] = “EGFR-TKI” AND
 - “Start date of this line (dd/mmm/yyyy)” [Second-line treatment period / TREAT. TREAT_start_date] is lower than or equal to (“Date of data collection (dd/mmm/yyyy)” [PI. PI_date_coll] – 11.50 months) AND
 - “EGFR mutations at start of first-line treatment” [First-line treatment period / MUT1. MUT1_unc] OR “EGFR mutations at start of second-line treatment” in the MUTATIONS form of the [Second-line treatment period / MUT2. MUT2_mut_start] has at least one of the options selected (excluding “Del19” and “L858R”) (*)

The therapy recorded in the field “Type of EGFR-TKI” [EAD. EAD_EGFR] of the EGFR-TKI ADMINISTRATION DETAILS form, having “Start date with this dose (dd/mmm/yyyy)” [EAD. EAD_start_date] equal to the start date of the Index EGFR-TKI therapy (defined before), will correspond to the Index EGFR-TKI therapy.

(*) *in case the option “Other EGFR mutation(s)” is selected, the Sponsor will evaluate plausibility (by means of a manual clinical review) of the specific mutation(s) recorded in the corresponding open field “If other EGFR mutation(s), please specify” [First-line treatment period / MUT1. MUT1_unc_sp], [Second-line treatment period / MUT2. MUT2_mut_start_sp]. The list of specified other EGFR mutations (if any) will be sent to Sponsor by the [REDACTED]*

- *Sequencing cohort*: it will correspond to the therapy recorded in the OSIMERTINIB ADMINISTRATION DETAILS form, having the earliest non-missing date recorded in field “Start date with this dose (dd/mmm/yyyy)” [OAD. OAD_start_date] lower than or equal to (“Date of data collection (dd/mmm/yyyy)” [PI. PI_date_coll] – 9.50 months). It is also required to have “EGFR mutations at start of second-line treatment” [Second-line treatment period / MUT2. MUT2_mut_start] including “T790M”.

NSCLC stage at start of first-line treatment

It will correspond to the field “Stage of disease at start of first-line treatment (or at NSCLC diagnosis, in case stage was not re-evaluated)” [**DIAG. DIAG_stage**], when this field is not missing. If this field is missing, but there is evidence that the patient was diagnosed with stage III (ie. the Investigator confirmed in a query that could not classify the tumor as IIIB or IIIC, but that the stage was not IIIA), then the patient will be classified as “stage III (unspecified B/C)”. As a result, the possible levels of this categorical variable will be:

- “stage IIIB”
- “stage IIIC”
- “stage III (unspecified B/C)”
- “stage IV”.

Duration of NSCLC until start of first-line treatment (in months)

It will be calculated as the difference between Start date of first-line therapy (as defined before) and Date of NSCLC diagnosis [**DIAG. DIAG_date**] + 1 day, divided by 30.4375 days.

Duration of NSCLC until start of index EGFR-TKI therapy (in months)

It will be calculated as the difference between Start date of the Index EGFR-TKI therapy (as defined before) and Date of NSCLC diagnosis [**DIAG. DIAG_date**] + 1 day, divided by 30.4375 days.

